### **Follow-up action after receiving a request to withdrawal:**

Upon receipt of request to withdrawal, the study staff will notify the Rady Children's Clinical Genome Center of the subject's withdrawal. In accordance with this protocol and the Genomics Institute Biorepository study protocol (IRB #160468), the following actions will be taken by both studies:

1. Ensure that unused blood from the participant is destroyed. Permanently break any link between personal identifying information and purified DNA and/or RNA from the participant. Isolated DNA and RNA that has not been sequenced will be destroyed in the event of withdrawal of a study subject.
2. Permanently break any link between personal identifying information and the anonymized records in the bioinformatic database by replacing PHI in the Master List with a note that the subject has withdrawn.
3. Not collect any additional clinical information about the individual from any source.
4. Only anonymized data may be used for future research after consent has been revoked.
5. Should a back-up of the inventory database/informatics system ever be restored, then the director should ensure that identifying records stored on the discarded samples log (that are relevant to the samples) are again deleted from the records.
6. Shred any hard copies of associated identifying information not required to be maintained for regulatory purposes.
7. Retain the executed consent form and request to withdrawal in a separate, secured file of discontinued subjects and redact any identifiers that link the subject to the data (such as subject number).
8. The Repository Director will certify that identifying links have been broken, that unused and unprocessed biological material has been destroyed.

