## **4. ESTIMATED DURATION OF THE STUDY**

Enrollment in Rady Children's Hospital acute care settings to begin in 2017 and to continue through 2019, with follow-up including chart review of outcomes through 2025.

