We may collect additional samples for functional studies needed to confirm genetic results. The sample amounts, types and additional family members who may be requested to provide additional samples will be determined on a case-by-case basis. Whenever possible, previously obtained clinical samples and/or samples stored in the Genomic Biorepository and/or RUB will be scavenged to avoid unnecessary patient blood draws. If additional samples are required that are not available from other studies or left-over clinical samples, families will be contacted regarding these research-only additional samples. The specific sample type and amount will be discussed with each family and permission will be requested prior to any additional research-only sample collection. Additional samples that may be collected for research-only purposes include blood, buccal swabs, saliva, non-invasive stool collection, and/or a clean-catch urine specimen. The study team will coordinate collection of such samples, and whenever possible, will coordinate these collections to overlap with routine clinical care. No charges will be applied for research-only sample collection. We may also use non-invasive methods of DNA collection to test the sample accuracy against whole blood.

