## **Surveys:**

### **Family Surveys:**

After enrollment into the research study, families will have a brief survey administered assessing their trust in medical providers (see appendix). In-person surveys will be given the option to take the survey on paper independently or administered by research staff verbally. Families for whom a translated survey is not available will have the survey administered using an interpreter. Families will receive two follow-up surveys (see appendix) assessing decisional regret and perceived benefits or harm of testing. The first follow-up survey will be administered within one week of the return of results (including the return of no results), and the second follow-up survey will be administered approximately one year after enrollment. If families are still in the hospital at the time of follow-up, research staff will attempt to meet the families bedside to conduct the survey. For families that are no longer in-patient at the time of follow-up, research staff will attempt to contact families by phone prior to administration of follow-up surveys and families will be offered the choice to decline further

surveys at that time. Barring a verbal decline for further surveys, families will have the choice to take the survey electronically e.g. via a REDCap survey or by phone. Families who chose the electronic survey will be told that if the survey is not completed within 72 hours, the research staff will contact them to conduct the survey by phone, with a possible second contact at a scheduled time.

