### **Withdrawal of consent:**

Participation in this study is completely voluntary. As part of the parental permission/assent/consent process, participants are informed that they can withdraw consent at any time, for any reason. If at any time, a patient decides to withdraw consent, personnel at the bio bank will take appropriate steps to respect the will of the participant and ensure that the participant is able to withdraw without reprisal.

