### **Proprietary Interest Disclosure/ Moore Clause:**

Consent into this study requires participants to agree to giving blood or tissue specimens, these specimens will become the property of the Genomic Institute. [name] or designee will be responsible for deciding how samples and collected data will be used. [name] and his associates or his successors in these studies will keep specimen, DNA, clinical data and/or the information derived from the specimens indefinitely. If as a result

of participation in this study, the study team obtains information that could significantly affect a participant's health and well-being, we will attempt to inform the participant of the existence of this information. The information obtained from this testing will be kept completely confidential to the extent permitted by law.

The specimens, the DNA they contain, and the clinical data collected may be used in this research and in other research, and may be shared with other organizations. In addition, de-identified data will also be shared with public databases sponsored by the National Institutes of Health and other agencies, and possibly with future scientists that are not known at this time. The specimens could lead to discoveries or inventions that may be of value to RCIGM or to other organizations. These discoveries or inventions may have significant commercial value. Under state law, participants do not have any right to money or other compensation stemming from products that may be developed from the specimens.

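### A withdrawal request triggers one all-or-nothing procedure, with no level that keeps passive chart review and vital status

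*Combined protocol and SAP*

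**What the plan says.** Section 12, under Withdrawal of consent, says in general terms that personnel will "take appropriate steps to respect the will of the participant". The next subsection, on follow-up action after a request, turns this into one numbered list that both this study and the biorepository must carry out. Two items matter most here: "Permanently break any link between personal identifying information and the anonymized records in the bioinformatic database", done by replacing the identifiers in the Master List with a note of withdrawal, and "Not collect any additional clinical information about the individual from any source". On data already held, the list says "Only anonymized data may be used for future research after consent has been revoked". No lesser level of withdrawal is described.

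Outside withdrawal, some things can be refused one at a time. Under Family Surveys (section 9): "Barring a verbal decline for further surveys, families will have the choice to take the survey electronically". For extra specimens, under Recruitment, Enrollment and Sample Collection: "permission will be requested prior to any additional research-only sample collection". Neither passage says that refusing ends chart review.

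Section 4 puts enrolment in 2017 to 2019, "with follow-up including chart review of outcomes through 2025". Patient clinical information (section 9) schedules collection at one year and then annually. Data Analysis (section 9) lists QALYs, DALYs, mortality and severe morbidity as outcomes, and Sample size determination (section 10) calls QALYs a key primary outcome.

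**The concern.** Chart review asks nothing of the family, yet it carries the long-term outcomes. A family whose only wish is to be left alone may express that as a request to withdraw. The protocol then gives staff one response, and that response also ends the passive follow-up the family might have been content to leave running. Co-enrolment adds another route. The withdrawal steps apply to both studies together, and the text describes no way for a family uneasy about sample storage or data sharing to leave the biorepository while trial follow-up continues.

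The main risk is bias rather than lost precision. Background and Significance (section 7) expects WGS to yield more diagnoses than WES. If families leave more often after a negative result or a poor prognosis, the infants with missing long-term outcomes could differ between arms. That link is plausible but is not shown in the documents. No rule was found for analysing withdrawn infants or missing outcomes, and a broken link cannot be restored.

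**Working it through.** **1. Follow-up lost per infant (section 4).** The horizon is 2025 − 2019 = 6 years to 2025 − 2017 = 8 years. Withdrawal about one year after enrolment loses 6 − 1 = 5 to 8 − 1 = 7 years. Earlier withdrawal loses more.

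**2. Number affected.** No withdrawal rate is given, so 3% to 8% is an assumption. Of the maximum of 1,000 infants, that is 30 to 80. Of the approximately 250 that section 10 expects by September 2019, it is about 8 to 20.

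**3. Worst-case bounds on the mortality difference.** Let a fraction w of each arm withdraw with vital status unknown afterwards. Each arm's risk then lies between (known deaths)/n and (known deaths)/n + w. With D the difference in known-death proportions, the true difference lies between D − w and D + w.
- w = 3%: 15 of 500 unknown per arm, bounds ±3 points
- w = 5%: 25 of 500 unknown per arm, bounds ±5 points
- w = 8%: 40 of 500 unknown per arm, bounds ±8 points

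These are extremes, reached only if every withdrawn infant in one arm died and none in the other. They do not shrink as the sample grows.

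**4. Power for the clinical utility index (CUI), the only comparison the plan sizes.** Inputs from section 10: 50% versus 40%, alpha 0.05, 80% power, 325 per arm stated, 500 per arm proposed. First, the plan's own figure:

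n = [z(α)·√(2·0.45·0.55) + z(β)·√(0.25 + 0.24)]² / 0.10²

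- One-sided: (1.645·0.7036 + 0.842·0.7)² / 0.01 gives 305; with continuity correction, 325. This matches the plan.
- Two-sided: (1.960·0.7036 + 0.842·0.7)² / 0.01 gives 388; with continuity correction, 408.

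The one-sided basis of the 325 is a separate matter. Removing withdrawn infants altogether from 500 per arm gives:

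| Assumed loss | n per arm | Power, two-sided | Power, one-sided |
|---|---|---|---|
| 0% | 500 | 0.890 | 0.938 |
| 5% | 475 | 0.874 | 0.928 |
| 10% | 450 | 0.856 | 0.916 |
| 20% | 400 | 0.813 | 0.886 |

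The sample falls to 388 per arm at 1 − 388/500 = 22.4% loss, and to 325 at 1 − 325/500 = 35%. If CUI rests on the clinician survey due within a week of results, even this overstates the damage, because most withdrawals would probably come later.

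**5. QALYs.** The effect on power cannot be computed. Section 10 gives 2.9 QALYs saved per infant for rapid trio WGS, but no standard deviation and no WES value.

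**The case against.** The strongest reply is that stopping collection and unlinking after consent is revoked protects participants and is not an error, and that families already have most of what a lesser level would give them. Much of this stands. Full withdrawal should keep its present steps. A reader might infer that no partial option exists at all. The documents do not support that: surveys and extra samples can be refused separately, and no research visits are scheduled. What is missing is a lesser level at the moment a withdrawal request is made.

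Other stronger readings also fail:
- **Earlier data are discarded.** They are not; anonymised data may still be used. The text refers to future research, though, and does not say that these data stay in this trial's randomised comparison.
- **Arm and day of withdrawal become untraceable.** This is not shown. The Master List keeps a note of withdrawal, and the redaction of subject numbers applies to the retained consent form and request. Nothing orders the arm erased, but nothing requires the arm or the date to be kept either.
- **Link-breaking contradicts the promise on health-relevant findings.** The Moore Clause subsection says "we will attempt to inform the participant of the existence of this information", without addressing people who have withdrawn. Confirmation runs through a clinical order to the medical record, samples under confirmation keep identifiers, and urgent diagnoses are reported before confirmation. At most this is an edge case to clarify.

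The mortality concern is also softened because many deaths come early: section 7 reports 57% mortality by 100 days (12 of 21) among diagnosed infants in a previous cohort. A death before withdrawal is already known. Finally, consent pages are not in the review copy and the biorepository protocol was not available, so a tiered choice may exist there.

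**Conclusion.** The point holds in a limited form and is a low-cost improvement. As written, the protocol gives up passive outcome data for every withdrawn infant from the withdrawal date, without asking whether the family would leave chart review in place. The size is unknown. The ±3 to ±8 points on mortality rest on an assumed 3% to 8% withdrawal in each arm and on extreme outcomes among those infants. Bias in Aim 1 further requires that withdrawal be related to diagnosis or prognosis, which is a possibility and not a finding.

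A reader might infer that withdrawals threaten the trial's power. The figures do not support that for CUI at 500 per arm, which tolerates about 22% loss before falling below the two-sided requirement. That reserve depends on reaching 500 per arm, and it does nothing for bias or for QALYs, whose power cannot be assessed.

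**What to change.** In the two withdrawal subsections of section 12, and in the consent form if it does not already do so, define two levels and present them neutrally, with neither offered as the default:

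- **Level (a):** no further contact, surveys or samples; chart review and vital status continue.
- **Level (b):** full withdrawal with the current steps. Only this level triggers link-breaking.

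State that data collected up to withdrawal stay in the as-randomised comparison, and that the anonymised record keeps the assigned arm and the day of withdrawal. Clarify how the withdrawal steps apply to results still pending, so that they read consistently with Return of Results (section 9) and the Moore Clause subsection.

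The cost is a protocol amendment, a consent-form amendment if needed, and a short withdrawal form. Staff must explain two levels to families, and the IRB must approve the wording.

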### **Proprietary Interest Disclosure/ Moore Clause:**

Consent into this study requires participants to agree to giving blood or tissue specimens, these specimens will become the property of the Genomic Institute. [name] or designee will be responsible for deciding how samples and collected data will be used. [name] and his associates or his successors in these studies will keep specimen, DNA, clinical data and/or the information derived from the specimens indefinitely. If as a result

of participation in this study, the study team obtains information that could significantly affect a participant's health and well-being, we will attempt to inform the participant of the existence of this information. The information obtained from this testing will be kept completely confidential to the extent permitted by law.

The specimens, the DNA they contain, and the clinical data collected may be used in this research and in other research, and may be shared with other organizations. In addition, de-identified data will also be shared with public databases sponsored by the National Institutes of Health and other agencies, and possibly with future scientists that are not known at this time. The specimens could lead to discoveries or inventions that may be of value to RCIGM or to other organizations. These discoveries or inventions may have significant commercial value. Under state law, participants do not have any right to money or other compensation stemming from products that may be developed from the specimens.

### **13. ALTERNATIVES TO STUDY PARTICIPATION**

The alternative to this study is to not participate in this study.

### **14. POTENTIAL RISKS**

Risks associated with blood draws include pain, anxiety, bleeding, bruising, or possibility of fainting or infection.

Slight risk of loss of confidentiality.

Risk of discrimination associated with genetic testing.

Genetic testing may cause anxiety or emotional distress due to feelings of responsibility for carrying genetic components passed on to children.

Risk of secondary or incidental findings being determined.

### **15. RISK MANAGEMENT PROCEDURES AND ADEQUACY OF RESOURCES**

Whenever possible, samples for this study will be obtained from clinical samples to minimize risk and invasive procedures. All sample collection will be obtained by qualified staff following the hospital guidelines and standard precautions.

All study related material will be stored securely. All identifying information will be kept in a separate database with access limited to study personnel. All data will be maintained in password protected, secure databases and or internal servers with access limited to study personnel and approved investigators.

Information regarding the protections and limitations of the Genetic Information Nondiscrimination Act (GINA) will be included in the consent.

Genetic counselors will be a part of the study team and will be available to all participants at all times while enrolled in the study to answer questions or concerns related to testing or results.

This study does not intend to report matters of paternity, carrier statuses or other secondary findings.

As the inclusion of pregnant women is for the purpose of improving clinical outcomes for the living affected infant, study participation is considered minimal risk. Blood draws and sample collection from the mother may be done independently for research or with routine clinical care.

Study auditing and monitoring will be conducted internally. The PI will periodically review the collection, storage, and distribution practices associated with this data bank and determine whether changes to enhance

confidentiality and privacy are required. Annual progress reports will be conducted and available to the IRB. All protocol deviations will be reported to the PI and the IRB as soon as identified. In the unlikely event of a serious adverse event or breach in confidentiality, the event will be reported to the IRB within 48 hours of it becoming known to the PI.

External auditing and monitoring by members of the NIH and/or FDA will be conducted per agency request. DSMB will monitor study through NIH consortium.

Any employees of the hospital who are eligible to participate will be consented by a study team member who is not their direct supervisor and, whenever possible, not a coworker or acquaintance of the staff member. Employees will be notified that participation or refusal to participate will in no way affect their employment status.

All clinical testing and therapy appropriate to the study participant's care will be continued without disruption during the study. The clinicians are initially blinded to the randomization and will continue all clinical testing regardless of whether rapid genomic sequencing is performed.

## **16. PRIVACY AND CONFIDENTIALITY CONSIDERATIONS INCLUDING DATA ACCESS AND MANAGEMENT**

### **Subject Confidentiality-**

Research personnel will identify patients meeting inclusion criteria via daily census review as well as through recommendations of clinicians and a list from MIT. Upon enrollment, each medical record will be reviewed by research staff and data entered into the research record. All genomic sequencing and biospecimens will be performed and maintained under the Genomic Institute Biorepository protocol (IRB #160468).

All research records and genomic sequencing data will be electronically stored in a password protected database accessible only to research personnel. HIPAA identifiers of all study subjects will be kept in a password protected database and will be linked only with a study identification number for this research. All computer entry and networking programs will be done using study identification numbers only. All data will be entered into a computer that is password protected. All sequencing data and biospecimens will be stored securely under the Genomic Institute Biorepository protocol (Study #160468). Clinical information will not be released without written permission of the subject, except as necessary for monitoring by IRB, the FDA, the OHRP, the Sponsor, or the Sponsor's designee. Data will be stored in a locked office of the investigators and maintained for a minimum of three years after the completion of the study.

### **Records to be kept**

Information will be collected on a data collection sheet for each patient participant (Appendix) and stored in a password protected relational database. A master linking list will be maintained that links the subject's medical record number with their study number (Appendix). De-identified genomic sequencing data will be stored in a password protected relational database.

### **Secure Storage of Data**

The research record generated will consist of an excel sheet and/or secured REDCap database. Only the data points listed will be entered into the data collection sheet (Appendix). Security measures include: storage of the password protected excel sheet on a password protected computer in a restricted access departmental folder limited to only listed study personnel and/or in a secured, password protected REDCap database with access limited to research study members.

All study related material will be stored securely. Access to research records, pre-screening logs, and the master

list will be limited to study personnel and maintained securely with password protection on a secure internal server.

Surveys may be sent via email by REDCap to clinicians and family members. Study information, personal identifiers, such as name, MRN, and contact information will be stored in REDCap. The survey functionality of REDCap does not allow survey participants access to any other REDCap data or forms.

Participant and clinician survey data will be collected by researchers at RCIGM/RCHSD. The data will be stored in a secure, HIPAA compliant, password protected database such as REDCap, within the RCIGM server. The IT department from RCIGM will send de-identified data to UCSD to be stored and analyzed on the UCSD secured server.

All samples and data will be stored de-identified in the Genomic Institute Biorepository (IRB #160468).

All transfer of study related information between sites will be done securely without identifying information whenever possible.

